Statistical Plan

Glucocorticoid Antagonist Treatment of Alcohol Use Disorder

From NIH Grant Application #AA023152

P.I. [name].

Submitted 2/7/2014

All analyses will be conducted in the intention-to-treat sample with $p<0.05$ for two-tailed tests of significance. Demographics and baseline measures will be examined for differences between treatment groups and tested individually for correlation with each outcome. Any baseline variable significantly associated with outcome or differing between treatment groups will be included in subsequent analyses as a covariate. Trend dose effects will be determined using single or multi parameter tests of Mixed Effect Model (MEM) effects, as required. All MEMs are repeated measures centered on the relevant time period. Time, treatment, and time x treatment will be evaluated as fixed effects in each model.

Mifepristone plasma concentration and baseline drinking levels were significant predictors of response in our Proof of Concept (POC) study and will be evaluated as predictors in the proposed study. Sex, age, age of onset and family history of alcoholism will be examined as covariates of response because of a potential association with cortisol in the case of the latter 3 variables and to assess differential treatment response for males and females, given mifepristone's antiprogestrone effects, and the trend for females to have better drinking outcome in our POC study. Motivation, e.g., to have abstinence as a treatment goal, will be examined as a non-specific predictor of treatment outcome. Potential pharmacogenetic predictors of response will be evaluated on an exploratory basis.

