Furthermore, a collaboration with [name], Director, Neurogenetics Lab, NIAAA, will permit an exploratory evaluation of genetic predictors of response; the high affinity of mifepristone for the glucocorticoid receptor makes mifepristone a good candidate for pharmacogenetic analysis that may guide future studies and clinical applications.

GENERAL INVESTIGATIONAL PLAN

SUBJECTS

Sample Size

Power and sample size estimates are based on the change in the number of drinks per week found in our POC study that involved 1-week of mifepristone 600 mg/d vs placebo in 50 subjects with AUD and in our 12-week clinical trial of gabapentin 900mg, 1800mg and placebo in 150 subjects with AUD.² Repeated measures ANCOVA performed on the change in number of

drinks per week from baseline through Week 5 in the POC study found significant ($F=3.82$, $df=2$, $p=0.03$) slope effects between mifepristone (-9.19, SEM 7.5) and placebo (+3.62, SEM 7.5), yielding a Cohen's $d=0.485$ (medium effect size). Continuous outcomes will be assessed for trend dose effects. Based on estimates of change of 0, -2.2 and -6.7 (SE 1.6) drinks per week for placebo, 900mg and 1800mg, respectively, in our gabapentin study, the test for linear trend contrast resulted in highly significant ($p<0.001$) linear trends with post hoc power at least 99% at the target alpha. Power calculation of cumulative mean drinks per week vs. dose with a planned linear contrast indicates that with 50 subjects per arm (placebo, low dose, high dose), and means which decrease by at least 32% as dose increases, we achieve 91% power to detect a non-zero contrast of the means versus the alternative that contrast is zero using an F test. These calculations assume an alpha=0.05, a common SD \pm 12, and hypothesized means of approximately 16, 11 and 8 drinks per week based on the gabapentin data. Estimating early termination by approximately 40% subjects based on clinical trials of similar design,^{2,3} the same power analysis for a conservative total of 30 subjects per arm indicates 82% power to test the interactive term (week*treatment) at the alpha of 0.05.

Subject Characteristics

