A total of 150 subjects will be randomly assigned to 1 week of double-blind treatment with mifepristone 600 mg/d ($n=50$), 1200 mg/d ($n=50$) or placebo ($n=50$); all subjects will receive 8 weeks of counseling, 4 scheduled phone calls and a Week 12 follow up visit. Subjects will be medically healthy male or female volunteers, 18-65 years of age. Subjects must meet DSM-V criteria for current alcohol use disorder of moderate or greater severity, defined in DSM-V as ≥ 4 symptoms, because this is the level of severity likely to merit pharmacotherapy and to involve neuroadaptations in the stress systems that mifepristone is hypothesized to treat. Subjects must be abstinent ≥ 3 days (but ≤ 30 days) prior to randomization, as verified by the TLFB and BAC and have a CIWA ≤ 9 , to eliminate acute alcohol or withdrawal effects on study measures. Abstinence at randomization will be verified retrospectively by ethyl glucuronide/ethyl sulfate (EtG/Ets) testing, which can reliably detect alcohol metabolites in the urine 80 hours after alcohol consumption. EtG/Ets testing showed only 1 of 50 participants in our mifepristone lab study violated the 3-day abstinence requirement at baseline. Additionally, breathalyzer and Timeline Followback data are collected at every study visit; GGT data are collected monthly.

Inclusion Criteria:

- *Male or female volunteers, 18-65 years of age*
- *Meets DSM-V criteria for current alcohol use disorder of moderate or greater severity, defined by DSM-V as ≥ 4 symptoms*
- *In the month prior to screening, reports drinking > 21 standard drinks per week if male, > 14 if female, with at least one heavy drinking day (males: ≥ 5 drinks, females: ≥ 4 drinks) per week*
- *Seeking research-based outpatient treatment for AUD and willing to comply with the protocol, take daily oral medication for 1-week and complete 11 study visits*
- *Abstinent a minimum of 3 days (but not more than 30 days) prior to randomization*
- *Negative BAC and a CIWA score of ≤ 9 at randomization*
- *In acceptable health in the judgment of the study physician, on the basis of interview, medical history, physical exam, ECG, urine test and lab tests*
- *Females with childbearing potential must have a negative serum pregnancy test on the screening visit and a negative urine pregnancy test at randomization and agree to use non-hormonal effective birth control for the study duration and one month thereafter*

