This is a Phase II, single-site, randomized, double-blind, placebo-controlled, 3-arm, parallel groups, dose-ranging study of 1-week of treatment with mifepristone (0, 600, 1200 mg/d) given in conjunction with 8 weeks of manual-guided counseling, and a follow up visit at Week 12. Subjects will be 150 outpatient men and women seeking treatment for current AUD of moderate severity or greater, who are abstinent ≥ 3 and ≤ 30 days and not in acute withdrawal (CIWA ≤ 9) at time of randomization.

Initial Phone Screening: Clinically trained study personnel provide information about the study. Interested individuals who appear eligible are scheduled for a face-to-face intake evaluation.

Week -1, Screening: After providing written informed consent, subjects complete a Screening Visit for evaluation of eligibility (see Table 2). The Structured Clinical Interview for DSM-V (SCID-V) will be administered to determine the inclusion criteria of current AUD with ≥ 4 symptoms and to rule out AXIS I disorders that would warrant study exclusion. The subject's demographic information, medical and alcohol use history, and use of concomitant treatments will be recorded using standardized forms. Vital signs and breath alcohol concentration (BAC) will be assessed, and specimens for urinalysis, serum pregnancy test (if female), urine drug screen, blood chemistry that includes liver function tests (LFT's) and gamma glutamyl transferase (GGT), and complete blood count with differential (CBC w/diff) will be collected by the medical assistant and prepared for same day pick up by LabCorp for analyses. An electrocardiogram (ECG) will be performed. Subjects at risk of clinically significant symptoms of alcohol withdrawal (CIWA ≥ 9) are ineligible and will be referred for detoxification treatment. However, our community dwelling subjects typically do not require medical detoxification, and are advised to reduce their alcohol intake incrementally such that 3 consecutive days of abstinence are achieved prior to their baseline (Week 0) visit. The CIWA is then repeated at Week 0 to further rule out risk of significant withdrawal symptoms during double-blind treatment.

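### The dose-trend analysis and the 50/50/50, 1:1:1 design text were not updated, in the pages available, after the 600 mg arm was closed in favour of 1200 mg versus placebo

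*SAP*

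**What the plan says.** **Analysis.** The SAP, submitted 2/7/2014, says "Trend dose effects will be determined using single or multi parameter tests of Mixed Effect Model (MEM) effects, as required". It also says "All analyses will be conducted in the intention-to-treat sample", with two-tailed tests at 0.05, and enters time, treatment and their interaction as fixed effects in every repeated-measures model. The protocol's Sample Size section agrees on the trend: "Continuous outcomes will be assessed for trend dose effects".

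**Size and design.** The power calculation in Sample Size is for cumulative mean drinks per week "vs. dose with a planned linear contrast", "with 50 subjects per arm (placebo, low dose, high dose"), and reports 91%. Subject Characteristics says "A total of 150 subjects will be randomly assigned to 1 week of double-blind treatment", split 50/50/50. Procedures describes a "3-arm, parallel groups, dose-ranging study of 1-week of treatment with mifepristone (0, 600, 1200 mg/d"). Pharmacotherapy Conditions gives simple randomisation at 1:1:1.

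**Amendment.** Item 4.1 of the Request for Modification/Amendment removes 600 mg/day for the rest of the study and turns to 1200 mg/day against placebo. It says that both doses had been well tolerated up to then. An IRB notice marked as approved follows. The visible attachments are a revised consent form dated 1.9.18, training certificates and two articles.

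**The concern.** The amendment is the later document, so it governs the trial being run. The design and analysis text that can be read still describes the trial before it. Four things are left open: the statistical form of the main comparison, the number in each continuing arm, the ratio after closure, and the role of participants already given 600 mg.

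That last group exists, because the amendment reports tolerability of both doses, and it belongs to the intention-to-treat sample. If treatment enters the mixed model as a three-level factor, the treatment test has 2 df and draws on an arm that stopped recruiting early. Such a test does not isolate 1200 mg versus placebo. If a linear contrast is used instead, a result published as a dose trend would suggest evidence about 600 mg that the contrast does not carry. Leaving the choice open until data are seen is what an SAP should prevent.

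**Working it through.** **Inputs** (Sample Size section): means 16, 11 and 8 drinks per week for placebo, low and high dose; common SD 12; alpha 0.05, two-sided as in the SAP; one mean per subject, as in the cumulative-mean calculation.

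**1. Reproduce the stated 91%.** The protocol gives no coefficients. Equal dose spacing (0, 600, 1200) implies (−1, 0, +1), so the contrast is 16 − 8 = 8.
- Noncentrality = 8² / [12² × (1/50 + 1/50)] = 64 / 5.76 = 11.11.
- F test on 1 and 147 df: power **91.2%**, against 91% stated.

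The match supports the inferred coefficients. They give 600 mg zero weight, so this contrast is already 1200 mg versus placebo. A plain two-sample t-test at 50 per arm gives 91.0%.

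**2. The 2-df alternative at 50/50/50.** The grand mean is 35/3 = 11.67, and the squared deviations sum to 18.78 + 0.44 + 13.44 = 32.67 (before rounding).
- Noncentrality = 50 × 32.67 / 144 = 11.34.
- F test on 2 and 147 df: power **85.6%**.

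**3. 600 mg arm closed early.** The number on 600 mg is not given, so every possible value is covered.

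| Per continuing arm | On 600 mg | Contrast | 2-df test | Gap (points) |
|---|---|---|---|---|
| 50 | 1 to 50 | 91.0–91.2% | 84.5–85.6% | 5.5–6.5 |
| 30 | 1 to 30 | 71.9–72.4% | 60.9–62.6% | 9.7–11.0 |

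The 30 comes from the protocol's own allowance ("Estimating early termination by approximately 40% subjects"): 50 × 0.6 = 30. It treats early terminators as contributing nothing.

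**4. Two-arm power by size.** Noncentrality = n × 8² / (2 × 12²) = n × 64/288.

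| Analysed per arm | Noncentrality | Power |
|---|---|---|
| 30 | 6.67 | 71.9% |
| 37 | 8.22 | 80.8% |
| 50 | 11.11 | 91.0% |
| 65 | 14.44 | 96.5% |

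**5. What the unstated size could mean.** Assume that the total of 150 is kept, and that 600 mg closed after 30 to 135 participants had been randomised 1:1:1, with 1:1 afterwards. Each continuing arm then has 10 + 120/2 = 70 down to 45 + 15/2 = 52.5. Power is 97.5% to 92.3%, or 85.5% to 74.0% if only 60% of each arm is observed.

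**6. 600 mg versus placebo.** The difference is 16 − 11 = 5. At 50 per arm, noncentrality = 25 / 5.76 = 4.34 and power is 54%. An arm closed early would have less.

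The protocol's 82% at 30 per arm is for the week-by-treatment term. Its variance and correlation inputs are not given, so it is neither checked nor contradicted here.

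**The case against.** The strongest reply is that little is broken. The contrast used for power is already 1200 mg versus placebo. The SAP's fixed-effects model fits two arms as readily as three. The disputed sentence speaks of dose trends, and an omnibus test is not a trend test; in a repeated-measures model, several parameters may simply mean dose trend by time. All of this is fair. The 2-df power loss therefore depends on one reading. However, the fixed-effects sentence leads directly to that reading if treatment is a three-level factor, and nothing available rules it out.

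Two technical limits also stand. Zero weight for 600 mg is exact for the fixed contrast. For a fitted slope on dose it requires equal placebo and 1200 mg arms, which simple randomisation does not guarantee. At 55/30/45, in units of 600 mg, the mean dose is 120/130 = 0.923. The weights are then 30 × 0.077 = 2.3 for 600 mg and 45 × 1.077 = 48.5 for 1200 mg, a ratio of about 5%. Also, mixed models use data from before dropout, so 30 per arm is a worst case.

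A reader might infer that closing the arm invalidates the main test or costs it power. The figures do not support that if the contrast is used. A reader might also infer that the plan was never revised. Some pages of the amendment papers are unavailable, so that cannot be concluded, although the visible attachments include no revised protocol or SAP.

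**Conclusion.** The point holds as an inconsistency that should be fixed. In the pages available, the stated inference, arm sizes and ratio describe a three-arm trial, while the approved amendment describes a two-arm continuation with some 600 mg participants already in the analysis set.

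The size of the problem depends on the test chosen. With the linear contrast there is no power loss; what remains is a misleading label, unstated numbers and an undefined role for the 600 mg data. With a 2-df treatment test, the main comparison is not isolated and loses the power shown in step 3.

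This rests on the protocol's hypothesised means and SD, on one mean per subject rather than the repeated-measures model, on inferred contrast coefficients, and on no revision in the unavailable pages.

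**What to change.** Issue a dated SAP amendment, before unblinding if that is still possible, or point to an existing revision. It should:

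1. Make the 1200 mg versus placebo contrast from the mixed model, on the TLFB drinking outcome, the primary test among all participants randomised to those two arms.
2. Drop the dose-trend label and exclude a three-group 2-df test as a basis for the primary claim.
3. Report 600 mg as secondary or descriptive, compared with placebo participants randomised before closure.
4. Replace 50/50/50 and 1:1:1 with the actual ratio after closure and the number per continuing arm, and restate power (72% at 30, 81% at 37, 91% at 50 and 97% at 65 analysed per arm, on the assumptions above).

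A period term is needed only if the 1200 mg to placebo ratio changed at closure.

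The cost is a short document, with no new data or visits. The trade-off is no formal dose-response inference and low power for 600 mg.

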IND # 114497

Date submitted: July 2, 2014

Title: Glucocorticoid Antagonist Treatment of Alcohol Use Disorder

Responsible Investigator: [name].

INTRODUCTORY STATEMENT

Available medications for alcohol use disorders are of limited efficacy and grossly underutilized. Risk for relapse is highest in the first 90 days¹ and the development of safe and effective medications to increase rates of initial recovery in Alcohol Use Disorder (AUD) that can be implemented by a wide range of treatment providers is a high public health priority. With chronic heavy alcohol use and in alcohol dependence the neuroendocrine stress system becomes dysregulated, *i.e.*, the CORT response of the HPA axis becomes blunted and CRF systems in the amygdala become sensitized, conditions associated with greater craving and risk for relapse in protracted abstinence.

Mifepristone is a GR antagonist that, with 1-week of treatment, restores normal HPA feedback for prolonged periods across a range of disorders and ameliorates cognitive deficits associated with HPA axis dysregulation. Mifepristone produced dramatic effects in blocking compulsive alcohol seeking in animal models of alcohol dependence and protracted abstinence. Similarly, 1-week of treatment with mifepristone reduced cue- and stress-induced craving in a human laboratory POC study of risk factors for relapse in protracted abstinence, with significant effects on decreased drinking and craving persisting for 1-month post treatment in 50 non treatment seeking subjects with alcohol dependence relative to placebo. Improvement on tests of learning, memory and executive function were also found with mifepristone relative to placebo in our AUD sample. Mifepristone is FDA-approved for two indications and was well tolerated in our POC study in AUD and in studies involving 1-week of treatment aimed at "re-setting" the HPA/CRF axis at doses up to 1200 mg/d without titration. We propose to study a treatment seeking sample, with 1-week of mifepristone to increase rates of initial response by re-setting the HPA axis, followed by 8 weeks of counseling to consolidate and sustain medication effects. Based on the association between drinking outcome and mifepristone plasma concentration found in our POC study, we propose to conduct a 3-arm dose-ranging study with randomization to double-blind treatment with 600 or 1200 mg/d of mifepristone or matched placebo to identify optimal dosing for AUD.

Furthermore, a collaboration with [name], Director, Neurogenetics Lab, NIAAA, will permit an exploratory evaluation of genetic predictors of response; the high affinity of mifepristone for the glucocorticoid receptor makes mifepristone a good candidate for pharmacogenetic analysis that may guide future studies and clinical applications.

GENERAL INVESTIGATIONAL PLAN

SUBJECTS

Sample Size

Power and sample size estimates are based on the change in the number of drinks per week found in our POC study that involved 1-week of mifepristone 600 mg/d vs placebo in 50 subjects with AUD and in our 12-week clinical trial of gabapentin 900mg, 1800mg and placebo in 150 subjects with AUD.² Repeated measures ANCOVA performed on the change in number of

drinks per week from baseline through Week 5 in the POC study found significant ($F=3.82$, $df=2$, $p=0.03$) slope effects between mifepristone (-9.19, SEM 7.5) and placebo (+3.62, SEM 7.5), yielding a Cohen's $d=0.485$ (medium effect size). Continuous outcomes will be assessed for trend dose effects. Based on estimates of change of 0, -2.2 and -6.7 (SE 1.6) drinks per week for placebo, 900mg and 1800mg, respectively, in our gabapentin study, the test for linear trend contrast resulted in highly significant ($p<0.001$) linear trends with post hoc power at least 99% at the target alpha. Power calculation of cumulative mean drinks per week vs. dose with a planned linear contrast indicates that with 50 subjects per arm (placebo, low dose, high dose), and means which decrease by at least 32% as dose increases, we achieve 91% power to detect a non-zero contrast of the means versus the alternative that contrast is zero using an F test. These calculations assume an alpha=0.05, a common SD \pm 12, and hypothesized means of approximately 16, 11 and 8 drinks per week based on the gabapentin data. Estimating early termination by approximately 40% subjects based on clinical trials of similar design,^{2,3} the same power analysis for a conservative total of 30 subjects per arm indicates 82% power to test the interactive term (week*treatment) at the alpha of 0.05.

Subject Characteristics

A total of 150 subjects will be randomly assigned to 1 week of double-blind treatment with mifepristone 600 mg/d ($n=50$), 1200 mg/d ($n=50$) or placebo ($n=50$); all subjects will receive 8 weeks of counseling, 4 scheduled phone calls and a Week 12 follow up visit. Subjects will be medically healthy male or female volunteers, 18-65 years of age. Subjects must meet DSM-V criteria for current alcohol use disorder of moderate or greater severity, defined in DSM-V as ≥ 4 symptoms, because this is the level of severity likely to merit pharmacotherapy and to involve neuroadaptations in the stress systems that mifepristone is hypothesized to treat. Subjects must be abstinent ≥ 3 days (but ≤ 30 days) prior to randomization, as verified by the TLFB and BAC and have a CIWA ≤ 9 , to eliminate acute alcohol or withdrawal effects on study measures. Abstinence at randomization will be verified retrospectively by ethyl glucuronide/ethyl sulfate (EtG/Ets) testing, which can reliably detect alcohol metabolites in the urine 80 hours after alcohol consumption. EtG/Ets testing showed only 1 of 50 participants in our mifepristone lab study violated the 3-day abstinence requirement at baseline. Additionally, breathalyzer and Timeline Followback data are collected at every study visit; GGT data are collected monthly.

Inclusion Criteria:

- *Male or female volunteers, 18-65 years of age*
- *Meets DSM-V criteria for current alcohol use disorder of moderate or greater severity, defined by DSM-V as ≥ 4 symptoms*
- *In the month prior to screening, reports drinking > 21 standard drinks per week if male, > 14 if female, with at least one heavy drinking day (males: ≥ 5 drinks, females: ≥ 4 drinks) per week*
- *Seeking research-based outpatient treatment for AUD and willing to comply with the protocol, take daily oral medication for 1-week and complete 11 study visits*
- *Abstinent a minimum of 3 days (but not more than 30 days) prior to randomization*
- *Negative BAC and a CIWA score of ≤ 9 at randomization*
- *In acceptable health in the judgment of the study physician, on the basis of interview, medical history, physical exam, ECG, urine test and lab tests*
- *Females with childbearing potential must have a negative serum pregnancy test on the screening visit and a negative urine pregnancy test at randomization and agree to use non-hormonal effective birth control for the study duration and one month thereafter*
- *Subjects must be able to complete and understand questionnaires and study procedures in English and sign an informed consent*

- *Willingness to comply with the provisions of the protocol and take daily oral medication*

Exclusion Criteria

- *A medical condition that contraindicates the administration of mifepristone, such as:*
 - *history of adrenal failure, Addison's disease, or adrenal insufficiency*
 - *concurrent systemic corticosteroid therapy*
 - *hemorrhagic disorders*
 - *concurrent anticoagulant therapy*
 - *cardiovascular, hypertensive, hepatic, respiratory or renal disease*
 - *insulin dependent diabetes mellitus*
 - *severe anemia (< 12 hemoglobin)*
 - *inherited porphyria*
 - *females with history of unexplained vaginal bleeding, endometrial hyperplasia with atypia or endometrial carcinoma*
- *Significant medical disorders or clinically significant findings on ECG (e.g., prolongation of the QT_c interval), urine or blood tests that increase potential risk or interfere with study participation as determined by the Study Physician. Note: serum potassium below the normal range must be replaced to normal prior to randomization; individuals with serum potassium outside the range of normal will not be randomized*
- *Liver function tests more than 3 times the upper limit of normal or elevated bilirubin*
- *Female subjects with childbearing potential who are pregnant, nursing, or refuse to use effective non hormonal birth control for the 1-week of medication administration and one month thereafter*
- *Active suicidal ideation*
- *Meets DSM-V criteria for a major Axis I disorder including mood or anxiety disorders or substance use disorders other than alcohol or nicotine use disorders*
- *Positive urine drug screen at screening*
- *Treatment within the month prior to screening with an investigational drug or vaccine, or drugs that may influence study outcomes, e.g., disulfiram, naltrexone, acamprosate*
- *Chronic use or need for psychotropic drugs. Note: some drugs with psychotropic properties (e.g., anti-hypertensive drugs) are allowed if their use is judged by both the investigator and study physician not to pose a safety risk or impact the results of the study*
- *Current use of drugs that are CYP3A substrates and inhibitors (such as calcium channel blockers, azole antifungals, macrolide antibiotics, erythromycin, protease inhibitors) due to risk of interactions with mifepristone; CYP3A inducers (such as rifampin, rifabutin, rifapentine, phenobarbital, phenytoin, carbamazepine, and St. John's wort), which may decrease mifepristone exposure and possibly compromise efficacy or consuming grapefruit juice or chronic use of drugs that are CYP2C8/2C9 substrates (such as NSAIDs, warfarin, and repaglinide), or as determined by the Study Physician*
- *No fixed domicile and/or no availability by home or mobile telephone*
- *Treatment mandated by a legal authority*

Subject Recruitment and Retention

This is the first test of the clinical efficacy of mifepristone for AUD, and as such, requires recruiting individuals with AUD who are both treatment-seekers and free from clinically significant medical and psychiatric disorders or use of concomitant medications that could influence study outcomes. Our experience conducting two N=150, 12-week clinical trials in AUD

with similar admission criteria at Scripps reliably shows we must recruit about 5 subjects for each subject who is successfully randomized, resulting in a rate of randomization of approximately 33 subjects per year. This rate of randomization is consistent with the average rate of 30-36 subjects randomized annually by single sites in recent AUD trials with similarly restrictive admission criteria.

Per procedures established by NIAAA's Clinical Investigations Group,⁴ progressive incentive payments will be provided for attendance and completion of study assessments to enhance compliance with study procedures and retention. Subjects will earn a base rate starting at \$25 that will increase by \$5 for each subsequent consecutive visit. The 4 weekly phone calls will be compensated at a flat rate of \$10 each. Perfect attendance and participation in 4 phone calls will result in a subject earning \$590 over the 12 weeks of study and follow up.

PROCEDURES

This is a Phase II, single-site, randomized, double-blind, placebo-controlled, 3-arm, parallel groups, dose-ranging study of 1-week of treatment with mifepristone (0, 600, 1200 mg/d) given in conjunction with 8 weeks of manual-guided counseling, and a follow up visit at Week 12. Subjects will be 150 outpatient men and women seeking treatment for current AUD of moderate severity or greater, who are abstinent ≥ 3 and ≤ 30 days and not in acute withdrawal (CIWA ≤ 9) at time of randomization.

Initial Phone Screening: Clinically trained study personnel provide information about the study. Interested individuals who appear eligible are scheduled for a face-to-face intake evaluation.

Week -1, Screening: After providing written informed consent, subjects complete a Screening Visit for evaluation of eligibility (see Table 2). The Structured Clinical Interview for DSM-V (SCID-V) will be administered to determine the inclusion criteria of current AUD with ≥ 4 symptoms and to rule out AXIS I disorders that would warrant study exclusion. The subject's demographic information, medical and alcohol use history, and use of concomitant treatments will be recorded using standardized forms. Vital signs and breath alcohol concentration (BAC) will be assessed, and specimens for urinalysis, serum pregnancy test (if female), urine drug screen, blood chemistry that includes liver function tests (LFT's) and gamma glutamyl transferase (GGT), and complete blood count with differential (CBC w/diff) will be collected by the medical assistant and prepared for same day pick up by LabCorp for analyses. An electrocardiogram (ECG) will be performed. Subjects at risk of clinically significant symptoms of alcohol withdrawal (CIWA ≥ 9) are ineligible and will be referred for detoxification treatment. However, our community dwelling subjects typically do not require medical detoxification, and are advised to reduce their alcohol intake incrementally such that 3 consecutive days of abstinence are achieved prior to their baseline (Week 0) visit. The CIWA is then repeated at Week 0 to further rule out risk of significant withdrawal symptoms during double-blind treatment.

Week 0, Randomization: Subjects complete evaluation for eligibility. Study physicians review all laboratory results, EKG's, vital signs, medical and alcohol histories, use of illicit substances and concomitant treatments, and perform a physical exam to medically clear an individual for admission to study. Medically cleared subjects complete baseline assessments and are randomized to receive a 1-week supply of double-blind drug.

Weeks 1-8: Subjects complete weekly study assessments and counseling described below and in Table 2. Subjects will be seen by the same study personnel and have their visits scheduled at

the same time of day (typically midday) across the study to avoid effects of uncontrolled sources of variance on study measures.

Weeks 9-11: Weekly phone calls are scheduled to maintain contact with the participant and obtain TLFB data.

Week 12: Subjects complete a follow up visit to assess persistence of treatment effects on outcome and safety assessments. *Procedures to maximize the likelihood of participation in the follow-up visit include: scheduled weekly phone calls to maintain contact with subjects, paying for the follow up visit, obtaining multiple back-up addresses and phone numbers, to assist in locating subjects. Patients who are found to have relapsed, or who display other clinically significant symptoms, will be offered referral for appropriate treatment.*

Table 2. Schedule of Procedures for Study Visits

Scheduled Procedures Week	-1	0	1	2	3	4	5	6	7	8	12
Informed consent, demographics, medical and alcohol history, SCID-V	X										
Alcohol Dependence Scale; Fagerstrom Test for Nicotine Dependence; Illicit Drug Use Index; Childhood Trauma Questionnaire; Treatment Goals Checklist	X										
BAC, Vital signs Adverse events, Concomitant Medications	X	X	X	X	X	X	X	X	X	X	
Pregnancy test ¹	X	X	X	X							
Clinical Institute Withdrawal Assessment-Revised (CIWA)	X	X									
CBC w/diff, blood chemistry ² , UA, UDS	X		X		X					X	X
ECG			X								
Plasma cortisol, ACTH		X	X	X		X				X	X
Mifepristone plasma concentration				X							
Alcohol Craving Questionnaire (ACQ); Timeline Follow Back Interview (TLFB); Pittsburgh Sleep Quality Index (PSQI); Beck Depression Inventory-II (BDI-II), State-Trait Anxiety Inventory (STAI)	X	X	X	X	X	X	X	X	X	X	
Neurocognitive Assessment, EtG/EtS			X								X
Physical exam, saliva and WBC for pharmacogenetics, dispense study drug			X								
Manual-guided counseling	X	X	X	X	X	X	X	X	X	X	

¹ Females of child-bearing potential only, with serum pregnancy at Week -1 and urine at Week 0, 2 and 3.

² Chemistry panel to include: Glucose, GGT, ALT, AST, alkaline phosphates, bilirubin, uric acid, serum creatinine, BUN, electrolytes, calcium, inorganic phosphorus, total protein and albumin. Only GGT and UDS will be obtained at Weeks 4, 8 and 12.

OUTCOME MEASURES AND ASSESSMENTS

Study Measures to Characterize the Sample:

Alcohol Dependence Scale (ADS)⁵ provides a reliable and valid quantitative measure of severity of alcohol dependence (Week -1, self-report, 5 minutes). Ethyl glucuronide/Ethyl sulfate (EtG/EtS): EtG/EtS's presence in urine can reliably detect alcohol metabolites in the urine 80 hours after alcohol consumption and will be used to retrospectively validate abstinence at randomization (Week 0). Childhood Trauma Questionnaire (CTQ)⁶ provides a reliable and valid retrospective measure of childhood abuse and neglect (Week -1, self-report, 5 minutes). Clinical Institute Withdrawal Assessment for Alcohol-Revised (CIWA-AR)⁷ is a reliable and valid scale to assess severity of alcohol withdrawal symptoms; scores ≥ 9 indicate pharmacological treatment may be warranted (Weeks -1 and 0, Study Physician or Research Nurse, 5 minutes).

Fagerstrom Test for Nicotine Dependence (FTND)⁸ is a 6-item rating scale of nicotine dependence (Week -1, self-report, 2 minutes). Illicit Drug Use Index⁹ is a composite index of frequency and duration of illicit drug use (Week -1, Study Clinician, 7 minutes). Standardized History form will record demography, medical and alcohol history, including age of onset of alcoholism, prior detoxifications, treatments and durations of abstinence, and family history of

alcoholism (Week -1, Study Clinician, 10 minutes). Structured Clinical Interview for the DSM V (SCID V; expected to be released in the winter of 2014 – <http://www.scid4.org>) will be used to establish the DSM-V categorical diagnosis of current alcohol use disorder of \geq moderate severity (≥ 4 symptoms) and to rule out exclusionary Axis I disorders¹⁰ (Week -1, Study Clinician, 30 minutes). Treatment Goals Checklist¹¹ is a 6-choice checklist subjects use to indicate their treatment goal, e.g., to quit drinking entirely, to quit but realizes a slip is possible, controlled use, etc. (Week -1, self-report, 2 minutes).

Primary Outcome Measure:

Timeline Followback Interview (TLFB)¹² provides quantity and frequency estimates of alcohol consumption for the 90-day period prior to and throughout study. A standard drink is defined as 14g of absolute ethanol content which is equivalent to 12 oz beer, 1.5 oz hard liquor or 5 oz wine.¹⁰ A heavy drinking day is defined as ≥ 4 drinks per day for women and ≥ 5 for men.¹⁰ TLFB drinking data will be supported with weekly drinking diaries as a memory guide, and validated by weekly breathalyzer determination, and monthly GGT values. If unresolved inconsistencies between sources occur, then the most negative outcome will be assumed accurate. (Assessment Coordinator, 10 minutes at Week -1, 5 minutes thereafter).

Secondary Outcome Measures:

Alcohol Craving Questionnaire-Short Form (ACQ-SF)¹³ provides an assessment of current drinking urges, difficulty resisting urge and anticipation of positive outcome or relief from negative affective state by drinking (every study visit, 2 minutes). Neurocognitive Functioning The California Verbal Learning Test-II (CVLT-II)¹⁴ and the Verbal Fluency, Trail Making, Color-Word Interference, Design Fluency and Towers tests from the Delis-Kaplan Executive Function System (D-KEFS)¹⁵ and Letter Number Sequences from the Wechsler Adult Intelligence Scale-IV (WAIS-IV)¹⁶ will be used to measure aspects of executive functioning, learning and memory, which are thought to be impacted by the hypothalamic-pituitary-adrenal (HPA) axis and alcohol use and to expand on the mifepristone POC study findings (Weeks 0 and 8, Neuropsychologist, 45 minutes).

Exploratory Measures:

Genetic Indicators of Mifepristone Effects Saliva samples will be collected using Oragene DNA (OG-500) 2 ml saliva kits (DNA Genotek, Inc) and genotyped on the Illumina Human Omni Express Exome beadchip, with analysis limited to selected candidate genes. Differences in response to mifepristone may also be reflected in cellular differences in response to the drug and to cortisol. To study this, blood samples will be collected and sent by same day transport to [name] Biochemical Genetics Laboratory at UCSD, which is located less than 1 mile from our lab and where peripheral white blood cells (PWBC's) will be extracted and cryopreserved. PWBCs will be isolated by density centrifugation through Nycoprep from whole blood (2 x 8ml) stabilized with acid citrate dextrose and stored at -140°C in tissue culture medium supplemented with 10% DMSO to maintain viability. [name] lab at NIAAA will generate lymphoblastoid cell lines and iPSC lines from cryopreserved PWBCs. Cell lines established from high and low responders to mifepristone will be analyzed for gene expression and methylation differences by RNA-seq and whole genome methylation analysis (Week 0, samples collected by Medical Technician). Cortisol and ACTH Blood is collected, spun, prepared, frozen and stored in [name] lab for periodic batch analysis in the [name]' lab using Enzyme Linked ImmunoSorbent Assay (ELISA) kits to provide quantitative determination of ACTH and cortisol in plasma (Weeks 0, 1, 2, 4, 8 and 12).

Safety Measures:

Breath Alcohol Concentrations (BAC) Subjects are informed prior to the screening visit that if they present with positive BAC's, they will not be paid and will be rescheduled, and have to wait until BAC is normal or will be accompanied home by a friend or taxi driver (beginning of every study visit, Research Nurse, 2 minutes). Adverse Event- Case Report form records each adverse event and onset, duration, severity, relation to study medication and clinical action (every study visit, Research Nurse, 5 minutes). Urine screen for illicit drug use (Weeks -1, 1, 4, 8 and 12).

PHARMACOTHERAPY CONDITIONS AND MEDICATIONS DISPENSED

Pharmacotherapy Conditions

Simple randomization procedures will be followed to randomly assign subjects to double-blind treatment with 600 mg/d or 1200 mg/d mifepristone or matched placebo in a 1:1:1 ratio, using a computer-generated randomization code provided by our laboratory biostatistician. Dose titration is not indicated.

